10.8 Recording Adverse Events

All Adverse Events occurring during the course of the study must be documented in the Adverse Event page of the electronic Case Report Form (eCRF). Moreover, if the Adverse Event is serious, the Serious Adverse Event Form must also be completed.

It is responsibility of the Investigator to collect all adverse events (both serious and non-serious) derived by spontaneous, unsolicited reports of patients, by observation and by routine open questionings.

For the purpose of this trial, “acute renal failure” occurrences will not be considered and recorded as adverse events, since well described as a part of the COVID19 syndrome, and highly prevalent in the involved population. They will be recorded as adverse events only if assessed as cause of patient’s death.

The recording period for Adverse Events is the period starting from the date of screening until the patient’s study participation ends.

Clinically significant abnormalities detected at study entry not due to a pre-existing condition or clinically significant changes at the following visits in the medical opinion of the investigator must be reported as adverse events in the eCRF.

If a clinically significant abnormal laboratory finding or other abnormal assessment meets the definition of an AE, then the AE eCRF page must be completed, as appropriate. A diagnosis, if known, or clinical signs and symptoms if diagnosis is unknown, rather than the clinically significant abnormal laboratory finding, should be reported on AE eCRF page. If no diagnosis is known and clinical signs and symptoms are not present, then the abnormal finding should be recorded.

For pharmacovigilance purposes, all SAEs should be followed-up in order to elucidate as completely and practically as possible their nature and/or causality until resolution of all queries, clinical recovery is complete, laboratory results have returned to normal, stable condition is reached or until the patient is lost to follow-up. Follow-up may therefore continue after the patient has left the study. In this case, the follow-up will continue with no timelines for related SAEs, while for unrelated SAEs the type and extent of follow-up undertaken will be determined for each individual case and will depend upon the nature (e.g. events with poor prognosis or which do not resolve), severity and medical significance of the event.

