1.3 Risk/benefit assessment

Detailed information about the known and expected benefits and risks and reasonably expected adverse events of porcine surfactant (Curosurf®), when used in neonates, may be found in the Investigator's Brochure of the drug.

The choice of dosing is based on prior beneficial adult ARDS studies [25][26][27][28], and the rapid pharmacodynamic response that would be expected if underlying surfactant inhibition or deficiency is a feature of COVID-19 disease.

Although adult ARDS trials have had some high-profile failures, investigation of fluid dynamic modelling and review of the original studies that showed efficacy suggests that larger fluid volumes and distal intrabronchial drug delivery are likely to be advantageous and may maximize alveolar surfactant delivery [29].

This trial will be conducted in compliance with the Declaration of Helsinki (1964 and amendments) current ICH E6 Good Clinical Practices and all other applicable laws and regulations.

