- ³ For mechanics assessments: blood sampling and tracheal aspirates (TA). Bronchoscopic washings performed as clinically indicated only, with surplus samples retrieved for mechanistic study as available. They are planned only for patients recruited in UK.
- ⁴ Blood count, bilirubin, creatinine, eGFR, glucose, AST, ALT, LDH, D-dimer, CRP (C-reactive protein), procalcitonin. Urine beta HCG at screening only.
- ⁵ SOFA score is calculated considering PaO₂/FiO₂, Glasgow coma scale, mean arterial pressure, and bilirubin, platelet and creatinine levels. SOFA score can be calculated only after the patient is included in the study (after the ICF signature) and in case not all the SOFA parameters are available before randomization, the calculation can be based on historical data collected (within 24 hours) as per standard practice.
- ⁶ Already available as part of the standard care procedures.
- ⁷ All screening procedures have to be completed/performed before the randomization.

The following time deviations from theoretical post-dose times will be allowed:

Post-dose time assessments	Allowed deviations
≤ 72 hours	± 1 hour
>72 hours	± 2 hours

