7.2.1 Laboratory assessments

7.2.1.1 Blood Sample Collection (as per [study schedule 7.1](#))

Blood samples (10 mls EDTA and 9 mls for Transfix) will be taken at intubation start as screening evaluation, then 24h after last treatment for poractant alfa group and 72h after randomization for control group. Then at Day 28 or at ICU discharge whichever occurs earlier. In particular:

- *Laboratory analysis*: blood count, bilirubin, creatinine, eGFR, glucose, AST, ALT, LDH, D-dimer, CRP, procalcitonin
- *Arterial blood gas (ABG) analyses*: approximately (~1 ml) of blood sample for the analysis of pH, pCO₂, pO₂, HCO₃, lactate will be taken at screening, before randomisation and 6,12, 24h after each administration up to 72 hours for poractant alfa group; before randomisation and at 6, 12, 24, 30, 36, 48, 54, 60, 72h after randomisation for control group. Then every 24 hours until day 28 or ICU discharge whichever occurs earlier
- *Mechanistic blood laboratory analysis*: inflammatory indices such as cellular and cytokine inflammatory markers and lipid mediators before randomisation and 12, 24, 48, 72, 96h after first administration (while hospitalised) and relative timepoints in the control group since randomization. These analyses are planned only in the UK subpopulation

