12.3.7 Safety variables

Adverse Events

The number of patients who experienced at least one AE, AEs related to poractant alfa (treated group) (ADRs), serious AEs (SAEs) and AEs leading to death will be summarized by group. Summaries will be presented overall (number and percentage of patients having at least one event, total number of events) and by system organ class and preferred term (number and percentage of patients having at least one occurrence of that event).

Clinical Study Code No.: CLI-050000-04	Version No.: 4.0
EUDRACT No.: 2020-002632-75 – IND No: 153286	Date: 02 MAR 2021

All adverse events will be listed.

Vital Signs

Vital sign values and their change from baseline will be summarized by group at each timepoint using descriptive statistics.

Laboratory data

Laboratory parameters and their change from baseline will be summarized by group at each timepoint using descriptive statistics.

All laboratory data will be listed.

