10.4 Laboratory Parameters

Laboratory parameters actual values and change from baseline will be presented using descriptive statistics by timepoint for each treatment group.

An individual subject listing will also be provided for laboratory data.

11 Other Analyses

No other analyses planned. All other data collected in the eCRF will be listed.

12 Changes in the Planned Analyses from Study Protocol

As this study is specifically linked to the COVID-19 pandemic situation, as there was a global improvement in the countries (US, UK, Italy) where the study was done during 2021 (vaccines against COVID-19, better treatment, variant less contagious...), the recruitment was lower than expected and the study was closed before reaching the target sample size of 70 subjects.

As a consequence all statistical analysis planned in the protocol were not done considering the low sample size:

- Statistical Analysis of Days Alive and Free from Ventilation at Day 21
- Subjects alive and free of respiratory failure at Day 28.
- Statistical Analysis of Days Alive and Free from Invasive Ventilation Day 28
- Statistical Analysis of Days Alive and Free from Invasive Ventilation at Day 21 and Day 28
- Statistical Analysis of Days Alive and Free from Non-Invasive Ventilation at Day 21 and Day 28
- Statistical Analysis of Mortality at Day 21 and Day 28
- Statistical Analysis of Proportion of Subjects with Improvement in Severity Status at Day 28/Discharge
- Statistical Analysis of Change from Baseline in pao₂/fio₂ Ratio at Each Timepoint
- Statistical Analysis of Proportion of Subjects with pao₂/fio₂ Ratio Improvement >20% Compared to Baseline at Each Timepoint
- Statistical Analysis of Change from Baseline in fio₂ at Each Timepoint
- Statistical Analysis of Length of ICU Stay (Days) at Day 28
- Statistical Analysis of Proportion of Subjects Alive and Out of ICU at Day 28
- Statistical Analysis of Delta SOFA Score at Day 3 and Day 28/ Discharge
- Statistical Analysis of Delta SOFA Sub Score at Day 3 and Day 28/Discharge
- Statistical Analysis of Proportion of Subjects Alive and Organ Failure Free at Day 28/Discharge

ITT definition was changed from “all randomised patients (analysed as randomised)” to “all randomised subjects who have at least one post baseline efficacy data analysed as randomised”.

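### Acute renal failure counts as an adverse event only if judged the cause of death; no by-arm count covers the other cases, and the SAP does not disclose the gap

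*Protocol*

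**What the plan says.** Protocol 10.8 states that acute renal failure "occurrences will not be considered and recorded as adverse events, since well described as a part of the COVID19 syndrome", and adds that it is highly prevalent in this population. One exception follows: "They will be recorded as adverse events only if assessed as cause of" the patient's death. There is no exception for a case that meets a seriousness criterion or that the investigator thinks related to the drug.

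The same section also requires that "clinically significant changes at the following visits in the medical opinion of the investigator must be reported as adverse events in the eCRF", with no renal exemption in that sentence.

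Renal function is measured elsewhere. The laboratory panel in Protocol 7.1 is "Blood count, bilirubin, creatinine, eGFR, glucose, AST, ALT, LDH, D-dimer, CRP (C-reactive protein), procalcitonin". Protocol 7.2.1.1 sets the samples at screening, then 24 hours after the last dose (treated arm) or 72 hours after randomisation (control arm). "Then at Day 28 or at ICU discharge whichever occurs earlier". SOFA, whose inputs include creatinine, follows the same pattern in the 7.1 schedule.

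Both documents plan a laboratory summary. Protocol 12.3.7: "Laboratory parameters and their change from baseline will be summarized by group at each timepoint using descriptive statistics". SAP 10.4: "Laboratory parameters actual values and change from baseline will be presented using descriptive statistics by timepoint for each treatment group".

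**The concern.** Whether the event is recorded depends on how it ends. The adverse event tables can therefore show renal failure only where it was judged to have killed the patient. In what follows, non-fatal means not assessed as the cause of death, so it includes patients who died of something else.

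A high background rate is a fair reason to exempt an event from individual reporting, because a single case says little. It is a poor reason not to count the event by arm, because the randomised comparison is then the only way to interpret it. Safety is part of the primary objective (Protocol 2.1, SAP 3.1). The risk section refers the reader to the "reasonably expected adverse events of porcine surfactant (Curosurf®), when used in neonates", so adult experience has to come largely from trials such as this one. A reader of the study report who sees few or no renal events could take that as a finding when it reflects the recording rule.

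**Working it through.** No figure in the plan bears on this point, so the check is a comparison of sections.

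1. **What depends on an adverse event record.** Under Protocol 10.8 the serious event form is completed only if an adverse event is serious. Intensity and causality (10.3, 10.4) are rated for adverse events. SAP 10.2 builds all its tables (emergent, serious, severe, drug reactions, leading to discontinuation, leading to death) from recorded events. A case that is not recorded is missing from every one of them. SAP 10.2, SAP section 12 and the adverse event table footnotes in SAP 16.1 do not mention the exclusion.

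2. **What the second rule in 10.8 restores.** Reporting clinically significant changes could bring in a raised creatinine. But 10.8 also says that a known diagnosis is to be entered in place of the laboratory finding. A raised creatinine with a known cause is thus routed to the excluded diagnosis, while an unexplained one can be entered. Sites could handle like cases differently, so what this rule recovers is unpredictable.

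3. **Renal information that is still summarised by arm.**

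| Output | Set | Timing | What it gives |
|---|---|---|---|
| Chemistry, SAP Table 14.3.4.3 | Safety | Screening, about 72 h, ICU discharge or Day 28 | Values and changes from baseline |
| SOFA sub-scores including kidney, SAP 9.3.10, Table 14.2.13 | ITT | As above | Values and changes from baseline |
| Concomitant procedures, SAP 8.5, Table 14.1.5.5 | Safety | All study periods in the schedule | Frequencies by SOC and PT |

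   The continuous summaries are n, mean, SD, median, minimum and maximum (SAP 7.8). There is no renal threshold, shift table or count of affected patients, and renal replacement is not named as an output. Two drafting faults add to this. The chemistry table's layout refers to a Table 14.3.6.1 that is not in the list. The Safety Set (SAP 6.1) requires a dose and is glossed as Curosurf-treated patients, which read literally removes the controls, although the table notes provide a control column.

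4. **Where each kind of case ends up.**
   - Judged the cause of death: in the adverse event tables.
   - Present at the 72-hour sample or at discharge/Day 28: moves a mean or a maximum, but is not counted.
   - Arises after 72 hours and needs renal replacement: in the procedure table, if the site enters it as a procedure.
   - Arises and resolves between samples with no recorded procedure: in none of these outputs.
   - Arises after 72 hours with no recorded procedure in a patient who then dies of another cause: in none of these outputs, since no discharge or Day 28 sample is to be expected.

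**The case against.** The exclusion is an explicit choice with a reason given, it applies to both arms, and fatal cases are kept. Following organ function through laboratory values and an organ score is a recognised alternative to event reporting. The SOFA table is on the ITT Set, so the Safety Set wording does not affect it. Procedures are reviewed throughout, so an episode needing renal replacement after Day 4 could be captured. The SAP is now wholly descriptive because the trial closed below 70 patients (section 12), so an extra count carries limited comparative information. Nothing in the documents points to a renal risk of this product.

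Much of this stands. A reader might infer that no renal comparison by arm exists, or that a renal signal in either direction could not be seen. The documents do not support that: three by-arm outputs carry renal information and deaths attributed to renal failure are tabulated. Detection is weaker, not absent. A reader might also infer that everything renal between Day 4 and discharge is lost; the procedure record contradicts that. Nor do the documents show bias between arms: the rule is the same for both, and the harm is lost information.

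Two parts do not stand. Disclosure in the protocol does not reach someone reading the report's tables. And means at sparse times do not answer how many patients in each arm had renal failure.

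**Conclusion.** The point holds as a limited reporting gap that is cheap to narrow. If sites followed Protocol 10.8 as written, non-fatal acute renal failure is absent from the adverse event, serious, severe and drug-reaction tables in both arms, the SAP does not disclose it, and no by-arm incidence of renal failure or renal replacement is specified. The existing renal summaries are partial substitutes.

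It would be tempting to put a number on the missing cases. The documents give neither an incidence of renal failure nor the share of cases that were fatal, and the planned arm sizes of 42 and 28 were not reached, so any number would be assumption throughout. The point does not need one.

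The conclusion assumes that sites applied the exclusion consistently. If some entered renal findings under the clinically-significant-change rule, the gap is smaller but uneven across sites.

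**What to change.** - **SAP 10.2 and 10.4:** add, by arm for all randomised patients, the number and percentage with a pre-specified worsening in creatinine or SOFA kidney sub-score, and the number with renal replacement recorded as a procedure. The sponsor should fix the criterion before the tables are run and show how many patients have no post-baseline sample. SAP section 12 refers to database lock as if already reached; if so, the study report should label these counts as added late.
- **Adverse event tables:** add a footnote that non-fatal acute renal failure was not recorded.
- **Protocol 10.8:** reconcile the exclusion with the rule on clinically significant changes. For the closed trial, state in the report how sites applied the two.
- **If the protocol is reused:** collect each episode in both arms on a disease-related-event page (start, intensity, relatedness, renal replacement), keeping any exemption from individual reporting. This cannot help the present trial, where enrolment is closed.

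Cost: one or two tables from data already collected and one footnote; some added site data entry only if the protocol is reused. The added counts would still miss episodes that fall between samples, which the footnote should also say.

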10.9 Reporting Serious Adverse Events to Chiesi

The Investigator must report all Serious Adverse Events in the SAE Form and provide it to the [REDACTED] email: [REDACTED], fax: [REDACTED], within 24 hours of awareness. The information must be sent by providing the completed Serious Adverse Event form. At a later date, the [REDACTED] Safety Contact will report all information to Chiesi Global Pharmacovigilance, the Clinical Project Manager and the Clinical Research Physician.

Clinical Study Code No.: CLI-050000-04	Version No.: 4.0
EUDRACT No.: 2020-002632-75 – IND No: 153286	Date: 02 MAR 2021

provided upon request. The [REDACTED] Safety Contact will inform Chiesi of the pregnancy within one working day of being notified.

- If the pregnancy's outcome meets the criteria for immediate classification of a SAE (e.g. spontaneous or therapeutic abortion, stillbirth, neonatal death, congenital anomaly, birth defect) the Investigator should follow the procedure for reporting SAEs.

11. DATA MANAGEMENT

An electronic CRF ([REDACTED]) will be filled-in by the Investigator and/or his/her representative designee. Screening failure data won't be recorded in the eCRF.

Front-end edit checks will run at the time of data collection and back-end edit checks will be used by the Data Manager to check for discrepancies and to ensure consistency and completeness of the data. Medical history, adverse events and concomitant procedures will be coded using the MedDRA dictionary; medications will be coded using the WHO Drug dictionary and Anatomical Therapeutic Chemical classification (ATC).

External data (laboratory assessments for mechanics assessments) will be processed centrally, sent to the designated CRO and reconciled with the corresponding information recorded in the CRF.

Access to electronic systems used for data collection will be granted to the study personnel only after appropriate training.

After the completion of data collection and cleaning, a review meeting will be held to determine the occurrence of any protocol violation and to define the patient populations for the analysis. Once the database has been declared to be complete and accurate, it will be locked and the planned statistical analysis will be performed.

If the database is unlocked after the initial lock, the process must be carefully controlled and documented; updates to the study data must be authorized by Chiesi.

At the study conclusion, a complete copy of the study data will be created for archival purposes at Chiesi. The investigators will receive copies of the patient data for retention at the investigational site documented; updates to the study data must be authorized by Chiesi.

12. STATISTICAL METHODS

12.1 Sample Size

A total of 70 patients will be randomised in the study with a ratio 3:2 (i.e. 42 patients randomised to the poractant alfa group and 28 in the control group). Assuming patients in the control arm being free from ventilation on average 1 week (i.e. 7 days), this sample size achieves 84% power to detect a difference of 4 days (i.e. on average 11 ventilation-free days for patients treated with poractant alfa), assuming a standard deviation of 5.5 and a two-sided significance level (alpha) of 0.05 using a two-sample t-test.

12.2 Populations for analysis

- **Intention-to-Treat population (ITT):** all randomised patients (analysed as randomised).
- **Safety population:** all randomised patients and receive at least one dose of the study treatment (Curosurf treated patients) (analysed as treated).

The primary analysis population for efficacy will be the ITT. The Safety population will be used in the analysis of all safety variables.

Clinical Study Code No.: CLI-050000-04	Version No.: 4.0
EUDRACT No.: 2020-002632-75 – IND No: 153286	Date: 02 MAR 2021

12.3 Statistical analysis

A detailed statistical analysis plan will be described in the Statistical Analysis Plan. The plan might be reviewed and updated as a result of the data review and will be finalized before database lock.

Intercurrent Events

Death and Early discontinuation from study drug can be anticipated as intercurrent events:

- Death will be incorporated as a failure outcome for binary endpoints using composite strategy;
- Early discontinuation from study drug will be handled using treatment policy strategy: all data collected after discontinuation from study drug till Day 28 or death will be included;
- Change in respiratory parameters will be analysed using while-alive strategy.

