6.6 Treatment Code

Study drug will be packaged and uniquely numbered. Each primary packaging in the medication kit will have a numbered label that matches the kit number on the label of the outside packaging.

This is an open-label study.

An individual randomization code envelope will be supplied to the Investigator for each patient and will contain the assignment treatment group for that patient. The Investigator will keep the treatment code envelopes in a locked, secure storage facility. Allocation of each patient to the assigned treatment group will be performed after opening the individual envelope associated with the lowest randomisation number.

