ITT	Intention-To-Treat
Max	Maximum
MedDRA	Medical Dictionary for Regulatory Activities
Min	Minimum
NIV	Non-Invasive Ventilation
PEEP	Positive End-Expiratory Pressure
PIP	Peak Inspiratory Pressure
Pplat	Plateau Pressure
PT	Preferred Term
RR	Respiratory Rate
rtPCR	Real Time Polymerase Chain Reaction
SAE	Serious Adverse Event
SAP	Statistical Analysis Plan
SBP	Systolic Blood Pressure
SD	Standard Deviation
SDTM	Study Data Tabulation Model
SARS	Severe Acute Respiratory Syndrome
SOC	System Organ Class
SOFA	Sequential Organ Failure Assessment
TA	Tracheal Aspirate
TEAE	Treatment Emergent Adverse Event
TV	Tidal Volume
UK	United Kingdom
vvECMO	Veno-Venous Extracorporeal Membrane Oxygenation

WHO	World Health Organization
WHO-DD	World Health Organization Drug Dictionary

VERSION HISTORY

Version	Date	Change History
0.1	07 Aug 2020	Not Applicable
0.2	01 Oct 2020	Updates following Chiesi review: Add of D21 mortality description, modification of Safety population definition.
0.3 (Stable version)	08 Oct 2020	Minor updates.
0.4	31 Aug 2021	Update according to protocol amendment. Protocol (protocol version 4.0, dated 02 March 2021). 
- The ECMO cohort has been removed- Central Laboratory assessments will be performed only for UK patients- Allowed Time windows have been identified and implemented- Clarify the inclusion of Death as intercurrent event in the primary endpoint- Key secondary endpoint added to comply with FDA request and guideline.- Additional timepoint for assessment added at Day 28 in line with FDA guideline.- New endpoints added to incorporate Death as intercurrent event in the evaluation
0.5	29 Jun 2022	Simplification of the analyses planned due to a lower recruitment. Slight update on footnotes and reference listings.
1.0	27 July 2022	Final version

1 Introduction

This document presents the Statistical Analysis Plan (SAP) for Chiesi Farmaceutici S.p.A. protocol CLI-050000-04: Multicenter, open label, randomised trial to assess the efficacy and tolerability of poractant alfa (porcine surfactant, Curosurf®) in hospitalized subjects with SARS-COV-19 acute respiratory distress syndrome (ARDS).

This analysis plan is based on the protocol (version 4.0), dated 02March2021 and the final electronic case report form (eCRF) (version 4.0) dated 03Jun2021.

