4.2 Safety Variables

- Adverse events (AEs).
- Laboratory parameters.
- Vital signs (blood pressures and pulse rate).

5 Sample Size

A total of 70 subjects will be randomised in the study with a ratio 3:2 (i.e. 42 subjects randomised to the poractant alfa group and 28 in the control group). Assuming subjects in the control arm being free from ventilation on average 1 week (i.e. 7 days), this sample size achieves 84% power to detect a difference of 4 days (i.e. on average 11 ventilation-free days for subjects treated with poractant alfa), assuming a standard deviation of 5.5 and a two-sided significance level (alpha) of 0.05 using a two-sample t-test.

6 Analysis Set

The definition of the analysis set is summarized below. A final agreement on the subjects to be included in or excluded from the analysis set will be reached during the review of the data

before database lock. Inclusions and exclusions from the analysis set will be fully documented in the Data Review Report.

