Cytospin analysis was not done by central laboratory University College London (UCL) due to freeze of the samples. Freezing destroys the cells in the TA samples and hence it has not been possible to do this analysis. Cytospin data won’t be summarized in the tables and will be listed as missing in the listings.

Data on inflammatory indices such as cellular and cytokine (pg/ml) inflammatory markers (e.g. IL-1, IL-6, TNF alpha, IFN gamma and lymphocyte markers) from TA and blood samples were not provided (i.e., not analysed by the time of DB lock). As a consequence, these won’t be summarised and listed.

13 Output

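### The pre-lock data review of this open-label trial is not described as masked, yet it may change the SAP and settle the analysis sets; ITT should be fixed by the randomisation list

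*Protocol*

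**What the plan says.** Protocol 6.6 states: "This is an open-label study". Protocol 11 places the data review late ("After the completion of data collection and cleaning") and gives it this task: "a review meeting will be held to determine the occurrence of any protocol violation and to define the patient populations for the analysis". Protocol 12.3 then leaves the SAP open: "The plan might be reviewed and updated as a result of the data review and will be finalized before database lock".

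The SAP gives the same review several decisions:

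- **Analysis sets.** SAP 6 says that agreement on "the subjects to be included in or excluded from the analysis set will be reached during the review of the data". SAP 8.1.3 has important deviations discussed there for their effect on the analysis populations.
- **Missing data.** Critical missing data not covered by the rules are discussed there (Protocol 12.3.2, SAP 7.4).
- **Timepoints.** Re-allocation of unscheduled readings is decided there (SAP 7.11).

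On ITT, Protocol 12.2 takes everyone randomised. SAP 6.2 requires in addition some efficacy value after baseline. SAP 12 discloses this ("ITT definition was changed from" the protocol wording to the new one) without giving a reason. SAP 7.13 still describes ITT as identical to the randomised set.

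The SAP version history has an entry of 29 Jun 2022 for v0.5, "Simplification of the analyses planned due to a lower recruitment", and v1.0 is dated 27 July 2022. No entry mentions ITT. No database-lock date is given.

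**The concern.** Finalising a SAP before lock protects against result-driven choices only if those making the choices cannot see results by arm. Lock freezes values; it does not hide them. Here the arm is known, the Day 21 and Day 28 outcomes are already in the database when the review meets, and the review can affect who is analysed, how gaps are handled and what the plan says.

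At stake is the standing of the final SAP as pre-specified. In a small trial that closed early, a few decisions about membership or data handling could also move the reported means and percentages in either direction.

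**Working it through.** **1. Is masking described anywhere?** No. Visibility of arm is an inference, but a well-supported one:

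- Allocation is open (Protocol 6.6).
- The sponsor's own statistics and data management group prepares the randomisation lists (Protocol 6.5).
- Arm is built into the data. SAP 13.2.1 labels timepoints by first dose in one arm and by randomisation in the other, and SAP Listing 16.2.5 holds dosing records for one arm only.

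**2. What can the review decide, and what limits it?**

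| Decision | Source | Limit in the text |
|---|---|---|
| Update the SAP | Protocol 12.3 | Final before lock; changes disclosed (SAP 12) |
| Membership of sets | Protocol 11; SAP 6, 8.1.3 | Written definitions; Data Review Report |
| Critical missing data | Protocol 12.3.2; SAP 7.4 | No imputation by default; documented |
| Re-allocating readings | SAP 7.11 | Nominal timepoint by default; justified in the report; all readings listed |

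SAP 7.12 adds that all collected data will be used. These controls record or narrow the decisions. None of them hides arm or outcome from those deciding.

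**3. Does ITT need a meeting?** Under Protocol 12.2, no: the randomisation list settles it. Under SAP 6.2 someone must judge what counts as an efficacy value after baseline, which the SAP does not define. SAP 8.1.3 also lets deviations bear on the populations, although there is no per-protocol set and the ITT definition does not depend on deviations. The review's remit is therefore wider than the ITT definition requires.

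**4. Can the ITT change be dated?** No. The version history logs a change to the Safety population at v0.2 but none to ITT at any version. SAP 6.2 and SAP 7.13 coincide only if every randomised patient has a post-baseline efficacy value, which the documents do not state.

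**5. Scale.** The planning figures are 42 against 28 patients, a difference of 4 days and SD 5.5. They give 4 / (5.5 × √(1/28 + 1/42)) = 4 / 1.342 = 2.98. Power is 83.6% from the exact noncentral t with 68 df and 84.6% from the normal approximation, so the stated 84% is reproduced.

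As a purely hypothetical yardstick, removing k zero-score patients from an arm of n with mean m raises its mean by n·m/(n − k) − m. With n = 42 and k = 2:

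- m = 7: 42 × 7/40 − 7 = 0.35 day, or 0.35/4 ≈ 9% of the planned difference.
- m = 11: 42 × 11/40 − 11 = 0.55 day, or 0.55/4 ≈ 14%.

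This is not an estimate of bias in this trial. A zero comes from death or from ventilation throughout the period (SAP 4.1.1). Both are outcomes observed after baseline, so such a patient belongs in ITT under Protocol 12.2 and, on a natural reading, under SAP 6.2.

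**The case against.** The strongest reply is that open-label describes treatment, not the listings used at the data review. No passage says that outcomes by arm were seen, and the Data Review Report is not among the documents. This stands: a reader might infer that the changes followed the results, but the documents do not support that. The reason given for cutting the analyses is low recruitment, every planned model was replaced by description (SAP 7.5, 12), and the ITT change is disclosed.

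A reader might also infer that the SAP was finalised after lock, because SAP 12 says that inflammatory-marker data "were not provided (i.e., not analysed by the time of DB lock". That sentence concerns outstanding assays, in a section that mixes past and future tense. Protocol 12.3 requires finalisation before lock, and without a lock date the order can be neither confirmed nor refuted.

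Some of the discretion is also small. Defaults exist for missing data and timepoints. The primary endpoint comes from ventilation dates and death (SAP 9.1), so re-allocating readings does not touch it.

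Finally, full masking would not work. Safety-set membership, study-intervention deviations and dose-timed readings need dosing data, and missing ventilation or death data cannot be reviewed with those outcomes removed. That objection is sound and limits the remedy. It does not explain why ITT membership should be open to agreement at all.

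**Conclusion.** The point holds as a gap in safeguards, not as evidence of bias. In an open-label trial, the documents leave SAP changes, set membership and residual data handling to a late review, describe no masking of it, and rely on controls that document decisions without shielding them. The ITT set was narrowed at an undated point and is described inconsistently within the SAP.

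No effect size can be assigned. The mean shifts shown above would need exclusions that the written definitions do not permit. Because the final SAP reports descriptive statistics only, inflation of type I error does not apply to its outputs. Set membership and handling rules still affect the reported summaries. The conclusion rests on the inference that arm was visible at the review and on the absence of a stated lock date. It is a low-cost improvement and does not invalidate the trial.

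**What to change.** 1. In Protocol 11 and SAP 6, state that ITT membership is fixed by the randomisation list and is not decided at the review meeting. Reconcile SAP 6.2 with Protocol 12.2 and SAP 7.13.
2. Where feasible, take missing-data and re-allocation decisions by pre-stated rules, on listings without arm codes and without outcomes that the decision does not need (SAP 7.4, 7.11). Keep dosing data available where Safety-set membership, deviations or dose-timed readings require them.
3. State the database-lock date and when the ITT change was made. Label any change made after outcomes by arm had been seen as post hoc, and show the all-randomised result beside the modified set.

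Items 1 and 3 remain possible although recruitment has closed. The cost is minor wording and some programming of listings and a second summary; no patients are added.
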